3.3.3. Incidence of Transient Diarrhea in Diabetic Participants

- Name: Incidence of Transient Diarrhea in Diabetic Participants
- Definition: Number of diabetic participants experiencing transient diarrhea (resolving spontaneously without intervention or withdrawal) during the early treatment period (Days 1–3).
- Time Frame: Days 1–3
- Statistical Test: Not applicable for a single event or very rare events.
- Method: Descriptive reporting with qualitative context ("rare, <1% incidence"), as formal statistical analysis is not feasible or appropriate for isolated events.
- Effect Size: Not calculated.

4. Baseline Characteristics Analysis

- Descriptive statistics (mean \pm SD for continuous variables, n/% for categorical variables) will be used to summarize baseline characteristics for each treatment arm.
- Statistical tests (t-tests for continuous variables, chi-square tests for categorical variables) will be performed to confirm the balance of baseline characteristics between the Nimsai Herbal and placebo groups, ensuring randomization effectively distributed participant characteristics.

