2.3. Safety Objectives

- To determine the incidence of mild gastrointestinal discomfort (nausea, bloating, dyspepsia) in both treatment groups during the 10-day intervention.
- To assess the incidence of Serious Adverse Events (SAEs) in both treatment groups during the 10-day intervention.
- To determine the incidence of participant withdrawals due to adverse events in both treatment groups during the 10-day intervention.
- To specifically monitor and report the incidence of transient diarrhea in diabetic participants during the first three days of the intervention.

3. Study Design

3.1. Overall Design This is a prospective, randomized, double-blind, placebo-controlled, parallel-group clinical trial. Participants aged 18-70 years with symptomatic Grade 2-3 internal hemorrhoids will be randomized in a 1:1 ratio to either the Nimsai Herbal group or the placebo group. The intervention period will be 10 consecutive days.

[figure not shown]

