10.6. Safety Outcome Analysis

- Incidence of Mild Gastrointestinal Discomfort, SAEs, Withdrawals: Frequencies and percentages will be presented for both groups. Comparisons will be made using Fisher's Exact test for categorical data, particularly where low event counts are expected. Risk Differences with 95% CI will be reported.
- Transient Diarrhea in Diabetic Participants: This will be reported descriptively as the number and percentage of affected participants. No formal statistical test will be applied due to expected rarity.

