Statistical Analysis Plan (SAP): (Protocol NA-2024-01)

Official Title: Double-Blind, Placebo-Controlled, Parallel-Group Randomized Controlled Trial to Evaluate the Efficacy and Safety of Nimsai Herbal in Patients with Grade 2-3 Hemorrhoids

NCT Number: NCT07034820

Protocol Number: NA-2024-001

Document Date: October 10, 2021

Version: 2

Sponsor: Nimsai Academia Bursa, Türkiye

Principal Investigator: [name] Nimsai Academia

Center [contact]

Email: [contact]

Prepared by: Nimsai Academia Bursa, Türkiye

Submission Format: PDF/A

Confidentiality Statement: This document contains confidential information and is intended solely for authorized personnel, investigators, and regulatory authorities. Unauthorized reproduction or distribution is prohibited. No participant names or identifiable information are included.

1. Introduction

This Statistical Analysis Plan (SAP) outlines the detailed methodology for the statistical analysis of data collected during Protocol NA-2024-01, double-blind, placebo-controlled, parallel-group Randomized Controlled Trial evaluating the efficacy and safety of Nimsai Herbal in patients with Grade 2-3 hemorrhoids. This SAP is developed in conjunction with the study protocol (Protocol ID: NA-2024-01) and adheres to the principles of ICH Good Clinical Practice (GCP).

2. General Statistical Approach

- **Analysis Populations:** Analyses will be conducted on an intention-to-treat (ITT) basis, including all randomized participants regardless of treatment adherence or protocol deviations. A per-protocol (PP) sensitivity analysis will also be performed to assess the robustness of the primary findings, including only participants who completed the study as per protocol and had no major deviations.
- **Missing Data Handling:** Missing data for primary and secondary outcomes will be handled using appropriate methods, primarily multiple imputation if data are considered missing at random (MAR). Sensitivity analyses using Last Observation Carried Forward (LOCF) or complete case analysis will also be performed where appropriate.
- **Software:** Statistical analyses will be performed using validated statistical software, specifically SAS (Statistical Analysis System) or R.
- **Significance Level:** All statistical tests will be two-tailed, and a significance level of $\alpha=0.05$ will be used to determine statistical significance.

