3.3.2. Incidence of Serious Adverse Events (SAEs) and Withdrawals Due to Adverse Events

- Name: Incidence of Serious Adverse Events (SAEs) / Incidence of Withdrawals Due to Adverse Events
- Definition: Percentage of participants experiencing SAEs or discontinuing treatment/withdrawing due to AEs.
- Time Frame: Baseline to Day 10
- Statistical Test: Fisher's Exact test (if events occur)
- Method: Comparison of incidence data between groups. If no events are observed in either group, descriptive reporting will be provided (0% incidence).
- Effect Size: Risk Difference with a 95% CI.

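### SAP 3.3.3 writes in an incidence below 1% for transient diarrhea in diabetic participants before any data, with no denominator, arm split, interval or source

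*SAP*

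**What the plan says.** Protocol 2.3 lists as a safety objective "To specifically monitor and report the incidence of transient diarrhea in diabetic participants" over the first three days. Protocol 7.3.4 defines the event and gives a count of participants as its unit. Protocol 10.6 then says "This will be reported descriptively as the number and percentage of affected participants" and "No formal statistical test will be applied due to expected rarity". It gives no numerical expectation, and does not say what the percentage is taken over or whether it is split by arm.

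SAP 3.3.3 defines the outcome as a count of diabetic participants on Days 1-3. Its test field reads "Not applicable for a single event or very rare events", its method field supplies the wording "rare, <1% incidence", and no effect size is to be calculated.

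The neighbouring SAP 3.3.2, on serious adverse events and withdrawals, handles a similar situation differently: "If no events are observed in either group, descriptive reporting will be provided (0% incidence"). There the label depends on what is observed.

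**The concern.** An analysis plan should say how a result will be calculated and presented, not what the result will be. SAP 3.3.3 puts a numerical conclusion in the method field and presumes that events will be single or isolated. Nothing in either document supports the 1% figure, and no alternative wording is provided. SAP 3.3.2 attaches its preset label to a condition, whereas 3.3.3 attaches none to its number.

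The missing denominator decides whether the statement is true. Diabetics are the population named in the outcome and in the safety objective, but their number is not given. A reassuring phrase could therefore be printed next to data that contradict it, or next to data too sparse to support it, for a subgroup the protocol singled out for monitoring.

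**Working it through.** **Inputs.** Total enrolment is 300, 150 per arm (Protocol 3.3). Only uncontrolled diabetes is excluded (Protocol 4.2), so diabetics can enter, but no expected number is stated. Randomisation is stratified by hemorrhoid grade only (Protocol 6.1), so the split of diabetics between arms is not controlled. The stated figure is an incidence below 1%. It cannot be reproduced, because the documents give no event count, denominator, assumed rate or source.

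**Step 1: when is the label true as an observed proportion?** The condition is x/n < 0.01, that is n > 100x.

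- x = 0: always true.
- x = 1: needs n ≥ 101 (1/100 = 1.00% fails; 1/101 = 0.99% passes).
- x = 2: needs n ≥ 201.
- x = 3: 3/300 = 1.00%, so it fails even if every participant were diabetic.

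If the base were all 300 participants, 1/300 = 0.33% and 2/300 = 0.67% would both satisfy the label. The SAP does not say that this base is intended.

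**Step 2: plausible subgroup sizes.** I assume 15 to 60 diabetics, which is 5% to 20% of 300. This range is my assumption and does not come from the documents. For zero events the two-sided Clopper-Pearson 95% upper limit is 1 − 0.025^(1/n). The last column is 0.95^n, the chance of seeing no events if the true incidence were 5%, a value chosen only for illustration.

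| Diabetics, arms pooled | One event | Upper limit, zero events | P(zero events), true rate 5% |
|---|---|---|---|
| 15 | 6.7% | 22% | 46% |
| 30 | 3.3% | 12% | 21% |
| 45 | 2.2% | 8% | 10% |
| 60 | 1.7% | 6% | 5% |

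By arm, assuming a roughly even split:

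| Diabetics per arm | One event | Upper limit, one event | Upper limit, zero events |
|---|---|---|---|
| 8 | 12.5% | 53% | 37% |
| 15 | 6.7% | 32% | 22% |
| 23 | 4.3% | 22% | 15% |
| 30 | 3.3% | 17% | 12% |

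**Step 3: could zero events support a rate below 1%?** Solving 1 − 0.025^(1/n) < 0.01 gives n > ln(0.025)/ln(0.99) = 367.04, so at least 368 diabetics. The whole trial has 300, and 0/300 still has an upper limit of 1.22%.

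**Step 4: how easily would the label fail?** If the true rate were exactly 1%, the chance of at least one event is 1 − 0.99^n: 26% with 30 diabetics and 45% with 60. At either size, one event makes the label false.

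**The case against.** The phrase sits in parentheses and quotation marks and is called qualitative context, so it may be sample wording, or the expectation that justifies having no test. The reference to isolated events can be read as an implicit condition. Protocol 10.6 already requires a number and a percentage under a heading limited to diabetics, so a reader would see the true figure beside any label. The 15 to 60 range, the even split and the 5% rate are not in the documents. The interval calculations ask whether the trial could establish a population rate below 1%, which the SAP does not claim it will do. Finally, no document requires an interval for an untested descriptive count.

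Part of this stands. Leaving out a formal test is reasonable. The subgroup sizes are assumptions. The proof of error rests on the break-points in Step 1, while the interval figures only show how little a small subgroup can say. The exact interval is a recommendation and goes beyond the minimum correction.

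The rest does not remove the problem. A figure below 1% is quantitative whatever it is called. If it is illustrative, deleting it costs nothing; if it is the planned wording, it can be false. Even on the conditional reading, one event is a single, isolated event, and the label then fails with 100 or fewer diabetics. A percentage printed beside the phrase would expose the contradiction without resolving it. Taking all 300 as the base would dilute an outcome defined in diabetics, and the plan does not state that base.

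**Conclusion.** The concern holds. As written, SAP 3.3.3 supplies a numerical safety conclusion in advance, and that conclusion is false with one event among 100 or fewer diabetics, two among 200 or fewer, or three at any size this trial can reach. These break-points assume only that diabetics are the denominator. Under the further assumption of 15 to 60 diabetics, a single event would be 1.7 to 6.7 times the 1% ceiling, and zero events would leave an upper limit of 6% to 22%.

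The label is true of the sample with no events, or if all 300 participants were the base and there were at most two events. The consequence is limited to the reporting of one descriptive safety outcome. It should be corrected, but it does not bear on the primary comparison or the sample size.

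**What to change.** In SAP 3.3.3:

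- Delete the preset incidence phrase and the wording that presumes a single or isolated event.
- Leave the existing definition of transient diarrhea on Days 1-3 as the numerator.
- Name the denominator: all randomised diabetic participants. This matches the general basis in SAP section 2, "including all randomized participants regardless of treatment adherence or protocol deviations".
- Report by arm the number of diabetics, the number and percentage affected, and an exact (Clopper-Pearson) 95% confidence interval.
- Keep the outcome descriptive with no formal test, in line with Protocol 10.6.

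The cost is a few lines of SAP text. No new data are needed: comorbidities are recorded in the Day 0 medical history (Protocol 8.2), and diabetics already receive specific inquiry about this event (Protocol 7.3.4). The price in presentation is that the estimate will look as imprecise as it is and, if any event occurs, less favourable than the preset phrase.

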7.3.4. Incidence of Transient Diarrhea in Diabetic Participants

- Name: Incidence of Transient Diarrhea in Diabetic Participants
- Definition: The number of diabetic participants who experience transient diarrhea (defined as a temporary increase in stool frequency/looseness resolving spontaneously within 24-48 hours without requiring specific intervention or study withdrawal) during the first three days of the intervention.
- Time Frame: Days 1-3.
- Unit of Measure: Number of Participants.
- Assessment Method: Specific daily inquiry by investigators and recording in participant diaries and CRFs for diabetic participants.

8. Study Procedures and Schedule of Events

The study duration for each participant is 10 days of intervention, preceded by a screening period. All procedures will be meticulously documented.

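### SAP 3.3.3 fixes the descriptor for transient diarrhea in diabetic participants as under 1% before data exist and without a base, and neither document asks for this outcome by arm

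*SAP*

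**What the plan says.** SAP 3.3.3 defines the outcome as a number of diabetic participants with self-resolving diarrhea on Days 1 to 3. Its remaining lines are:

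- Test: "Statistical Test: Not applicable for a single event or very rare events".
- Method: descriptive reporting with the qualitative context "rare, <1% incidence", "as formal statistical analysis is not feasible or appropriate for isolated events".
- Last line: "Effect Size: Not calculated".

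The protocol treats the same outcome in three places:

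- Section 7.3.4 gives "Unit of Measure: Number of Participants" and collects the event by daily inquiry and diary, without limiting this to one arm.
- Section 10.6 states "This will be reported descriptively as the number and percentage of affected participants" and "No formal statistical test will be applied due to expected rarity". It does not say what the percentage is taken over and does not mention arms.
- Section 2.3, fourth safety objective, asks for the incidence without reference to the treatment groups.

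The other three safety outcomes (mild gastrointestinal discomfort, SAEs, withdrawals due to adverse events) are tied to both groups in the 2.3 objectives. In 10.6 they come under "Frequencies and percentages will be presented for both groups", and SAP 3.3.1 and 3.3.2 give them a risk difference with a 95% CI.

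**The concern.** An analysis plan should say how an incidence is computed, not what it will be. Here a figure is written in before any data, and its truth depends on a denominator that the SAP does not name. If it is carried into the report, it can contradict the trial's own count in the population that the outcome is about.

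The second gap is the missing arm. This is a named safety objective of a placebo-controlled trial. A result that satisfies the text need not show whether the events fell on active or placebo. Diabetes is not a stratification factor (protocol 6.1 stratifies by hemorrhoid grade only), so the arms may hold different numbers of diabetic participants, and bare counts by arm would not be enough.

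**Working it through.** **Inputs.** From the documents: 300 randomized, 150 per arm (protocol 3.3); stratification by grade only (6.1); uncontrolled diabetes excluded, other diabetes allowed (4.2). Not in the documents: the number of diabetic participants and any event count. I assume that 10% to 20% of the 300 are diabetic, so 30 to 60 in total and about 15 to 30 per arm.

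**The plan's own figure.** The under-1% figure cannot be reproduced, because neither document gives a numerator, a denominator or a number of diabetic participants.

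**When can the label be true?** It needs k/N < 0.01, that is N > 100k. The smallest N is 101 for one event, 201 for two and 301 for three.

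| Base | One event |
|---|---|
| 30 diabetic participants | 1/30 = 3.3% |
| 60 diabetic participants | 1/60 = 1.7% |
| 100 diabetic participants | 1/100 = 1.0%, not below 1% |
| 101 diabetic participants | 1/101 = 0.99% |
| all 300 randomized | 1/300 = 0.33% |

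With all 300 as the base, two events still fit (2/300 = 0.67%) but three do not (3/300 = 1.0%).

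**Would zero events establish it?** No. With no events the exact upper limit (97.5%, one-sided) is 1 − 0.025^(1/N): 11.6% for N = 30, 6.0% for N = 60 and 1.2% for N = 300.

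**Why N per arm is needed.** If D of the 300 are diabetic and diabetes is unrelated to allocation, the number in one arm of 150 is hypergeometric with mean D/2 and variance D × ½ × ½ × (300 − D)/299.

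- D = 30: variance 7.5 × 270/299 = 6.77, SD 2.60; the central 95% range is 10 to 20.
- D = 60: variance 15 × 240/299 = 12.04, SD 3.47; the range is 23 to 37.

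Two events in each arm is a difference of 0 points at 15 and 15. At 20 active and 10 placebo it is 2/20 − 2/10 = 10% − 20% = −10.0 points.

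**What an interval would add for an isolated event.** Take 1/15 active against 0/15 placebo. The Wilson 95% limits are 1.2% to 29.8% and 0% to 20.4%. Newcombe's method combines them:

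- lower: 6.67 − √((6.67 − 1.19)² + (20.39 − 0)²) = 6.67 − 21.11 = −14.4 points
- upper: 6.67 + √((29.82 − 6.67)² + (0 − 0)²) = 6.67 + 23.15 = 29.8 points

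At 30 per arm, 1 v 0 gives 3.3 points (−8.3 to 16.7). Neither interval says much beyond the by-arm counts.

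**The case against.** The strongest reply is that the phrase is only an expectation. The SAP sets it out as qualitative context, and protocol 10.6 likewise speaks of expected rarity. Protocol 10.6 also asks for an observed number and percentage, and the outcome's name makes diabetic participants the natural base. Nothing says that the label replaces the observed figures. This is fair, but it leaves the label in the SAP's reporting method with no base and no condition on the data. On the natural base it is contradicted by the first event unless there are more than 100 diabetic participants.

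The stake is also limited. The event is self-resolving by definition, every adverse event gets a causality rating (11.2), and diarrhea that is serious or leads to withdrawal is compared by arm elsewhere. Mild gastrointestinal discomfort is an open list compared by arm and may catch some of these events. It does not name diarrhea, is not confined to diabetic participants and runs to Day 10. These points hold and keep the matter small.

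Two stronger readings are tempting, and the documents do not support either:

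- A reader might infer that the SAP bars an effect estimate however many events occur, because its last line carries no condition. That line closes a block whose premise is single, very rare or isolated events, and it is most naturally read within that premise. For such events leaving out the estimate is defensible, as the 1 v 0 intervals show.
- A reader might infer that a pooled analysis is planned. Neither document calls for pooling. The text merely fails to rule it out.

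**Conclusion.** The point holds as a minor one, in two parts. First, the under-1% descriptor is fixed in advance with no base. It would be wrong for any non-zero count among 100 or fewer diabetic participants: 3.3% or 1.7% for a single event if there are 30 or 60. It could be rescued only by counting over all 300 randomized. Second, by-arm reporting is not written for this outcome, although it is for the other three, and without stratification by diabetes a count needs its own N in each arm.

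The threshold of 100 is arithmetic. The range of 30 to 60 and all event counts are assumptions, and with 101 or more diabetic participants one event would satisfy the label. The absence of a formal test is not at fault, and the absence of an effect size for isolated events is not an error.

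**What to change.** In SAP 3.3.3 delete "rare, <1% incidence" and put in its place: *diabetic participants with the event / all diabetic participants (n/N, %) by treatment arm; if there are no events, report 0/N by arm; no formal test.* Put the same sentence in protocol 10.6, and add to the fourth safety objective in 2.3 the reference to both groups that the other three carry.

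If events prove more than isolated, a descriptive risk difference with a small-sample 95% CI (Newcombe, for example) is an option, in line with what SAP 3.3.2 keeps for SAEs. It would be wide and should be read neither as a test nor as evidence of no difference. For example, an assumed 5/30 v 0/30 gives 16.7 points (2.0 to 33.6), which excludes zero, while Fisher's exact test gives p = 0.052.

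The cost is a few lines of wording in the two documents and one table row. Diabetic status, arm and diarrhea are already recorded.
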